All patients who discontinue the trial should complete an Early Termination Visit (see Table 2 and Table 3). For subjects who have a confirmed ALC below the 200 cells/ μ L limit and permanently discontinue from participation in the study, central laboratory testing will continue every 14 days (\pm 3 days) after the Early Termination Visit until it is above the lower limit of normal. With the exception of patients who withdraw consent or are lost to follow-up, patients should complete the 30-day and 90-day Safety Follow-up Visits for the collection of safety data and to assess their disease status. Alternative treatment for CD can be started, if needed, after the Early Termination Visit.

The reason for discontinuation of investigational drug will be recorded in the clinical records and the patient's eCRF. For those patients whose status is unclear because they fail to appear for trial visits without stating an intention to discontinue trial participation, the Investigator should

document in the source documents the steps taken to contact the patient (e.g., dates of telephone calls, registered letters) prior to withdrawing the patient from the trial.

Patients who withdraw from the trial will not be replaced.

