 - Hepatobiliary disorders
 - NASH
 - Cardiovascular causes
 - Concomitant treatments
- Macular edema
 - For patients with abnormal OCT findings or with visual signs or symptoms of new onset or worsening macular edema that develop following initiation of treatment, a general ophthalmologic examination including eye history, visual acuity, and dilated ophthalmoscopy will also be performed
 - Investigational drug must be discontinued in any patient who has a confirmed diagnosis of clinically significant macular edema that is of new onset or worsened since baseline
 - Patients with a diagnosis of macular edema must be followed up monthly and more frequently if needed based on the ophthalmologist's judgment
- Malignancies
 - Because RPC1063 is an immunomodulator, patients should be carefully monitored for infections and malignancies (including dermatologic malignancy)
 - The treating Investigator will complete a dermatological examination for monitoring of the potential development of new cutaneous malignancies during the trial. Patients with any suspicious finding noted during the examination will be referred to an appropriately qualified dermatologist for evaluation and treatment, if warranted
- Serious or opportunistic infections
 - TB, serious bacterial infections, systemic fungal infections, viral infections such as herpes infections (including herpes zoster and disseminated herpes simplex) and protozoan infections should be reported as AEs

- During the treatment period if a serious infection or a serious opportunistic infection is identified, investigational drug should be suspended until the patient has received appropriate treatment and has had resolution of the infection. Investigational drug can be restarted at the Investigator's discretion after assessment of the patient's clinical status (See Section 9.1.1 for instructions on resuming treatment after missing doses)
- Patients withdrawn from the trial as a result of the above will be followed until lymphocyte levels return to the patient's pre-treatment baseline or to the central laboratory's Lower Limit of Normal, whichever is lower

12.2.8. Monitoring of Patients with Adverse Events, Serious Adverse Events, and Adverse Events of Special Interest

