5.5.3. Visit Windows

The analysis time point assignment for the post-baseline visits will be assigned based on the analysis windows described in [Table 4](#) below for the following items:

- Efficacy (please see Protocol Table 2 for a description of what study elements are considered to belong to the Efficacy category; it is also noted that not all Efficacy elements are considered in this SAP, please see the endpoints in Sections 4.2.2, 4.2.3, and 12)
- 12-lead ECG
- Vital signs
- Hematology
- Blood chemistry
- Pregnancy test
- Urinalysis
- Physical examination
- Pulmonary function test
- Optical coherence tomography

Adverse events and coagulation panel data will not be windowed.

If multiple assessments are available within a range, then the one closest to the target day will be used for that analysis time point. If multiple assessments are same distance, but on different sides of the target day, then the latter one will be used. If multiple assessments are available on the same day, then the average of these assessments will be used, except for the lab and ECG data for which the assessment at a later time of the same day will be used.

Table 4. Analytic Visit Windows

Visit	Ideal Analysis Day^a	Visit Window
Baseline	1	<= 1
Week 4	29	2 – 42
Week 8	57	43 – 70
Week 12	85	71 – 98
Week 24	169	99 – 210
Week 36	253	211 – 294
Week 48	337	295 - 350
Week 52	365	351 - 392
Week 64	449	393 - 490
Week 76	533	491 - 574
Week 88	617	575 - 658

Week 100	701	659 - 742
Week 112	785	743 - 826
Week 124	869	827 - 910
Week 136	953	911 - 994
Week 148	1037	995 - 1078
Week 160	1121	≥ 1079
Safety Follow-up Day 30	30	≤ 60
Safety Follow-up Day 75 and Day 90	90	≥ 61

^aExcept for the visits recorded as safety follow-up visits, the reference date will be the date of the first dose of IP in the study, and the relative day is calculated date of assessment/collection – date of the first dose of IP + 1 if the date of assessment/collection is on or after the date of the first dose of IP, or date of assessment/collection – date of the first dose of IP if the date of assessment/collection is before the date of the first dose of IP. The reference date for the visits recorded as safety follow-up visits will be the date of the last dose of IP in the study, and the relative day is calculated date of assessment/collection – date of the last dose of IP.

Applying above visit window rules will be done after distinguishing treatment visits and follow-up visits by CRF visit labels.

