For all study elements to which the above table applies, the last available assessment will be derived as the last value on treatment, whether scheduled or unscheduled.

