10.2. Clinical Laboratory Evaluations

Laboratory assessments will be performed by a central laboratory. All summaries will be based on the standard international (SI) units provided by the central lab. Associated laboratory parameters such as hepatic profile, renal function, and hematology values will be grouped and presented together.

Summary tables for hematology, chemistry, and urinalysis including actual values and change and percent change values from Baseline will be presented for clinical laboratory tests collected as numeric values. These summaries will be provided for each visit, highest value, lowest value, and last value.

Hematology and blood chemistry values will be flagged as “low”, “normal”, or “high” relative to the normal ranges of the central laboratory. Categorical urinalysis values will be flagged as “normal” or “abnormal”. Categorical laboratory data will be summarized using shift tables where appropriate.

Laboratory data collected at unscheduled visits will be included in listings and will contribute to tables showing changes from Baseline to highest value, lowest value, and last value. The results from safety follow-up visit will not be included in the calculations of highest, lowest, and last values.

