APPENDIX 5. DOCUMENT REVISION HISTORY

Version	Date	Notes/Revisions
1.0	March 03 2016	Initial version.
1.1	November 23 2016	Updated with details and additional analyses.
1.2	January 26 2017	Updated with details on missing data and other details.
1.3	June 1, 2018	
Updated to reflect the Week 12 and Week 52 summary tables generated for topline analyses, definition of treatment failure, as well as to reflect endpoint alterations and additional details regarding CDAI, SES-CD, GHAS, and RHI algorithms. Analysis of compliance rate categories has been excluded.
 
Following endpoints have been removed from the SAP
 
 • PRO CD SF+AP response-25 • PRO CD SF+AP response-50 • PRO CD SF+AP response-30 + 2P • PRO2 CD response-25 • SF&AP clinical response-2 • SF&AP clinical response-1 • Endoscopic remission-2 • Histologic improvement • Histologic response 
Following endpoints have been added to the SAP
 
 • CRP-response-10 • FCP response-250 • Fistula Response • GHAS Improvement • GHAS Remission • RHI Improvement • RHI Response • RHI Remission • Global RHI Score • RHI Mucosal Healing
1.4	August 28, 2019	
LOCF removed.
 
Treatment Failure rule is used in NRI
 
Efficacy graphs added

1.5	January 06, 2020	
Changes from data review meeting
 
 • PFT abnormality has been revised • Missing segment imputation of SES-CD has been added

		
• Lower bound of 0 for Hematocrit sub-score of CDAI has been added• Treatment failure criteria has been revised• RHI response analysis on all patients has been removed• RHI remission by segment for subset of segment score > 3 is replaced by RHI remission by segment for non-RHI remitters• CRP Change among patients having CRP \geq 10 mg/L at Baseline has been added• Analysis window has been added to Safety follow-up visits• Unscheduled and early termination visits are included in all analysis windows• Patients requiring cardiac monitoring is determined programmatically• Listing of non-trial procedures added• Section on PK analysis is removed and combined with Section on PD• Description of SDTM data in Section 5 is removed
--	--	---

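### Post-discontinuation laboratory retests can fall into treatment-week rows and last values, because SAP 5.5.3 splits data by visit label and leaves on-treatment undefined

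*SAP*

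**What the plan says.** **How records are separated.** SAP Section 5.5.3 states: "Applying above visit window rules will be done after distinguishing treatment visits and follow-up visits by CRF visit labels". Footnote a to Table 4 then gives last dose one role only: "The reference date for the visits recorded as safety follow-up visits will be the date of the last dose of IP in the study". Every other record is dated from first dose and placed in a window from Week 4 to Week 160. Within a window, "If multiple assessments are available within a range, then the one closest to the target day will be used for that analysis time point".

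**Unscheduled records.** Section 5.5.3 does not exclude them. The version 1.5 entry in SAP Appendix 5 says "Unscheduled and early termination visits are included in all analysis windows". For laboratory data, SAP Section 10.2 assigns unscheduled results to listings and to the highest, lowest and last value tables. It does not mention the by-visit tables.

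**Last value.** Section 5.5.3 says "the last available assessment will be derived as the last value on treatment, whether scheduled or unscheduled" and does not define treatment for this purpose. Section 10.2 says "The results from safety follow-up visit will not be included in the calculations of highest, lowest, and last values" and names no other exclusion.

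**Tests after the drug is stopped.** Under Protocol Section 8.3, patients with a confirmed lymphocyte count below 200 cells/µL who stop permanently are tested every 14 days (±3), "after the Early Termination Visit until it is above the lower limit of normal". Protocol Section 12.2.7 also follows lymphocytes after withdrawal for serious or opportunistic infection. After Early Termination, Protocol Tables 2 and 3 have columns only for 30 and 90 days after last dose.

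**The concern.** The 14-day lymphocyte tests have no visit of their own, so unscheduled is a natural label for them. The label rule would then count them from first dose and treat them as treatment-week data, even though they are taken off drug to document recovery. Two draws on the same date could go to different rows: the one recorded as the 30-day visit to follow-up, the other to Week 12.

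The last-value summary has a related gap. Under Section 10.2, an unscheduled off-drug result is not excluded. Under Section 5.5.3 it should be, but only if treatment is read by date of last dose and not by visit label. The draw that ends the 14-day series is above the lower limit of normal by construction, so using it as a last value would show recovery where the table is meant to show the state on drug.

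The lymphocyte count is a pharmacodynamic endpoint (Protocol Synopsis), and SAP Section 10.2.1 tabulates counts below 200 and below 500 cells/µL by visit. Longer-term safety is the Extension Period's primary objective. The affected values would come from patients who stopped with severe lymphopenia.

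**Working it through.** The plan states no figure to reproduce; this is a data-handling rule. The check applies SAP Table 4 to example patients.

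**Inputs from the documents.** Week 8 is Days 43 to 70 (target 57), Week 12 is Days 71 to 98 (target 85), Week 24 is Days 99 to 210 (target 169), and the record nearest the target is used. Tests are 14 days apart (Protocol 8.3). Follow-up visits are at last dose +30 ±3 and +90 ±10 days (Protocol Table 2).

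**Assumptions.** Early Termination is 2 days after last dose. The 14-day draws are recorded as unscheduled. Unscheduled results enter by-visit tables. Testing continues long enough to reach the days shown.

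**1. Last dose Day 56, Early Termination Day 58.** Draws fall on Day 58 + 14k: Days 72, 86, 100, 114, 128, 142, 156.
- Week 12: |72 − 85| = 13 and |86 − 85| = 1, so Day 86 is used. 86 − 56 = 30 days off drug.
- Week 24: the nearest draw is Day 156 (169 − 156 = 13). 156 − 56 = 100 days off drug.

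**2. Other stopping days** (draws to about 90 days after last dose).

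| Last dose | Week rows filled off drug | Days off drug |
|---|---|---|
| Day 40 | Week 8 (Day 56), Week 12 (Day 84), Week 24 (Day 126) | 16, 44, 86 |
| Day 60 | Week 12 (Day 90), Week 24 (Day 146) | 30, 86 |
| Day 85 | Week 24 (Day 171); Week 12 keeps the on-drug Day 85 value | 86 |
| Day 365 | Week 64 (Day 451); Week 52 keeps the on-drug Day 365 value | 86 |

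An off-drug draw fills a row only where no on-drug value is nearer the target, so mainly in windows after the stop.

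**3. If draws near the follow-up visits carry the follow-up label.** In example 1 the 30-day visit spans Days 83 to 89 and the 90-day visit Days 136 to 156. If Days 86 and 156 are recorded as those visits, they are routed correctly. The unscheduled Day 72 draw then fills Week 12 (72 − 56 = 16 days off drug) and Day 142 fills Week 24 (142 − 56 = 86 days off drug). The misplacement shifts but does not disappear.

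**4. Last value, last dose Day 60.** Read by label, the last value is Day 146. With a cut-off at last dose, it is Day 57. With a cut-off of 7 or 14 days after last dose, it is the Day 62 Early Termination value, and the Week 12 and Week 24 cells are empty.

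**5. Size**, assuming 50 patients at a visit, 5 of them abnormal.
- One added normal value: 5/50 = 10.0% becomes 5/51 = 9.8%, a fall of 0.2 points.
- One added abnormal value: 6/51 = 11.8%, a rise of 1.8 points. The upper bound is about 1/50 = 2 points.
- With the SAP Section 5 default denominator (patients in the population, about 60), a normal value changes nothing and an abnormal one adds 1/60 = 1.7 points.

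**The case against.** The strongest reply is that the misplacement is conditional. The documents do not show what label the case report form gives the 14-day draws. The Appendix 5 note refers to all windows, which include the follow-up windows, so it does not by itself send these draws to treatment weeks. Section 10.2 does not name by-visit tables for unscheduled laboratory data. Sections 5.5.3 and 10.2 can also be read together, with the second adding to the first. All of this stands, and it limits the finding to what can happen.

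A reader might also infer that liver, lung and eye monitoring are affected to the same degree. The documents do not support that:
- The weekly liver tests in Protocol Section 12.2.7 follow any confirmed elevation and are not tied to discontinuation.
- Pulmonary evaluation after a respiratory discontinuation is as clinically indicated, with function tests only to be considered.
- Patients with macular edema "must be followed up monthly and more frequently if needed", but SAP Section 10.7 only lists tomography abnormalities, so no by-visit percentage can move.

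Any laboratory or pulmonary function retest that is done after permanent discontinuation meets the same rule. Only the lymphocyte tests are clearly required on a fixed schedule.

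Recovery values cannot erase a patient's lowest value or the overall counts below 200 and 500 cells/µL, and all data are listed by patient. The trial is descriptive, without hypothesis tests. These points bear on size. They do not supply the missing definition.

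**Conclusion.** The point holds in limited form. SAP 5.5.3 has no last-dose cut-off, its on-treatment wording is undefined, and it does not agree with 10.2. Off-drug lymphocyte tests, and any other laboratory or pulmonary function retest after permanent discontinuation, can therefore enter treatment-week rows. Off-drug laboratory results can also enter the highest and last values.

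This rests on the tests being recorded as unscheduled and, for the week rows, on unscheduled results being used in by-visit tables. Few patients are likely to qualify, although the documents give no count. Per patient, the effect is about 0.2 points for a normal value and up to about 2 points for an abnormal one, at an assumed 50 patients per visit; the upper figure would be about 4 points at 25 patients (1/25).

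A reader might conclude that reported lymphocyte suppression or liver abnormality will be materially diluted. The arithmetic does not support that: dilution comes from added normal values, where the effect is the smaller figure or zero. The point makes no claim about the SES-CD primary endpoint.

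**What to change.** In SAP Section 5.5.3, for laboratory, vital-sign, ECG and pulmonary function data:
- Define on-treatment as assessments up to last dose plus a short stated number of days. Always keep the Early Termination visit and the scheduled Week 12 or Week 160 end-of-treatment visit.
- Send later records to the existing follow-up windows (up to 60 days, and 61 days or more, after last dose), whatever their label.
- Use the same definition for the highest, lowest and last values in Section 10.2.
- State whether unscheduled laboratory results enter the by-visit tables.

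A cut-off on the day of last dose itself would be too strict. It could move a test done a day later into the 30-day follow-up row, and the Protocol's overview of changes ties the 90-day visit to metabolite clearance, so such a patient is not yet unexposed.

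The cost is SAP wording and one derivation from the last-dose date, which Section 8.2.1 already uses for exposure. A few values move from week rows to follow-up rows. The number of days is a convention to be chosen, since the documents give none. Off-drug tests during a temporary interruption precede the final dose and are not addressed. A late Early Termination visit can still fall in a later week: with last dose Day 85 and Early Termination Day 99, it falls in the Week 24 window.

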5.5.4. Handling of Missing and Partial Data

For all proportion-based efficacy endpoints, patients with missing efficacy data and the responses after treatment failure will be considered non-responders (NRI) in the primary analyses.

Treatment failures at Week 12 and Week 52 will be determined based on the rules listed in Section 9.1. In all analyses where NRI is used, responses of the patients who are treatment failures at Week 12 will be imputed as non-responder at Week 12 and onwards. In addition, responses of the patients who are treatment failures at Week 52 will be imputed as non-responder at Week 52 and onwards.

Continuous efficacy endpoints will not be imputed.

Sensitivity analyses on missing data on selected endpoints are detailed in the efficacy analyses sections 9.1 and 9.2.

With the exception of partial dates, missing demographic, disposition, baseline characteristics, medical history, and safety data will be analyzed using observed data only, without imputation. For

partial dates, the algorithms for imputation will vary depending upon the parameter; the details can be found in [Appendix 1](#).

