6.2.2. Extension Period Efficacy Endpoints

Patients in the Extension Period will be examined for the following efficacy endpoints:

- Proportion of patients in endoscopic remission based on SES-CD definitions at Week 52
- Proportion of patients in endoscopic response based on SES-CD definitions at Week 52
- Proportion of patients in clinical remission based on CDAI at Week 52
- Proportion of patients in clinical response based on CDAI at Week 52
- Proportion of patients in clinical remission based on PRO2 definitions at Week 52
- Proportion of patients in clinical response based on PRO2 definitions at Week 52
- Proportion of patients in clinical remission at Week 52 based on CDAI and PRO2 definitions who are off corticosteroids of those on corticosteroids at baseline
- Proportion of patients in clinical remission based on CDAI over time
- Proportion of patients in clinical response based on CDAI over time
- Proportion of patients in clinical remission based on PRO2 definitions over time
- Proportion of patients in clinical response based on PRO2 definitions over time

- Change in intestinal mucosa histopathologic features, histologic disease activity, and biomarkers over time
- Change in fecal calprotectin and serum C-reactive Protein levels over time
- Improvement in perianal and enterocutaneous fistulas in those patients with fistulas at baseline over time

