4.2.3. Efficacy Endpoints for Extension Period

The efficacy endpoints for the induction period listed above in section 4.2.2 will be evaluated for all extension visits.

In addition, proportion of patients achieving remission and remaining corticosteroid-free in the prior 12 weeks will be evaluated at each time point of Week 36, Week 48, and Week 52, among the patients who received corticosteroids for CD at baseline. This analysis will be performed for CDAI Remission and SF&AP Remission.

Clinical Remission (Based on CDAI) at both Week 12 and Week 52 will also be summarized. Following efficacy graphs will be presented.

- CDAI change from Baseline (Observed) showing mean and 95% CI at each scheduled visit up to Week 52, overall and by Biologic Exposed vs. Biologic Naïve
- CDAI (Observed) showing mean and 95% CI at each scheduled visit up to Week 160, overall and by Biologic Exposed vs. Biologic Naïve
- Bar graph of CDAI Clinical Response (NRI) at Week 12 and Week 52, overall and by Biologic Exposed vs. Biologic Naïve
- Bar graph of CDAI Clinical Response (Observed) at Week 12 and Week 52, overall and by Biologic Exposed vs. Biologic Naïve
- Bar graph of CDAI Clinical Remission (NRI) at Week 12 and Week 52, overall and by Biologic Exposed vs. Biologic Naïve
- Bar graph of CDAI Clinical Remission (Observed) at Week 12 and Week 52, overall and by Biologic Exposed vs. Biologic Naïve
- Bar graph of Endoscopic Response-50 (Paired Segments, NRI) at Week 12 and Week 52, overall and by Biologic Exposed vs. Biologic Naïve
- Bar graph of Endoscopic Response-50 (Paired Segments, Observed) at Week 12 and Week 52, overall and by Biologic Exposed vs. Biologic Naïve
- Stool frequency change from Baseline (Observed) showing mean and 95% CI at each scheduled visit up to Week 52, overall and by Biologic Exposed vs. Biologic Naïve
- Stool frequency (Observed) showing mean and 95% CI at each scheduled visit up to Week 160, overall and by Biologic Exposed vs. Biologic Naïve

- Abdominal Pain change from Baseline (Observed) showing mean and 95% CI at each scheduled visit up to Week 52, overall and by Biologic Exposed vs. Biologic Naïve
- Abdominal Pain (Observed) showing mean and 95% CI at each scheduled visit up to Week 160, overall and by Biologic Exposed vs. Biologic Naïve

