9.1. Treatment Failure Rules

Final Treatment Failure status will be determined by internal clinical review using the following rules:

1. Any protocol-prohibited change in CD medications including the following:
 - a. Post-baseline initiation of, or increase in, corticosteroids to treat worsening CD to a dose greater than the maximum daily dose taken between the Screening and Baseline visits
 - b. Prolonged course of systemic corticosteroids > 14 days for treatment of disease other than CD
 - c. Initiation of an immune-suppressing therapy including 6-mercaptopurine (6-MP), azathioprine, anti-TNF agents, or vedolizumab
 - d. Post-baseline initiation of antibiotics to treat worsening of CD/disease flare
2. Surgical resection of small intestine or colon during the study as a treatment of CD-related symptoms
3. Endoscopic dilation treatment for CD-associated stricture(s) during the study

Treatment failures at Week 12 and Week 52 will be determined by using the above rules. Treatment failure status will be used as a criterion in NRI. Patients identified as Treatment Failures will be listed.

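### SAP 5.5.4 makes every response after treatment failure a non-response, but its mechanics start only at Weeks 12 and 52, so the other by-visit NRI tables can count rescued patients as responders

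*SAP*

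**What the plan says.** SAP 5.5.4 begins with a general rule for every proportion-based endpoint: "patients with missing efficacy data and the responses after treatment failure will be considered non-responders (NRI) in the primary analyses". It names no visit. Two further sentences, introduced as covering every analysis that uses NRI, give the mechanics: "responses of the patients who are treatment failures at Week 12 will be imputed as non-responder at Week 12 and onwards", and "responses of the patients who are treatment failures at Week 52 will be imputed as non-responder at Week 52 and onwards". Section 9.1 uses the same two landmarks: "Treatment failures at Week 12 and Week 52 will be determined by using the above rules". The events that make a patient a failure are not tied to those visits. One is "Post-baseline initiation of antibiotics to treat worsening of CD/disease flare"; others are new or increased corticosteroids, immune-suppressing therapy, bowel resection and stricture dilation.

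Binary results are planned at other visits too. Protocol 6.2.2 lists "Proportion of patients in clinical remission based on CDAI over time", with matching items for CDAI response and for PRO2 response and remission. SAP 4.2.3 says: "The efficacy endpoints for the induction period listed above in section 4.2.2 will be evaluated for all extension visits". It adds corticosteroid-free remission, which "will be evaluated at each time point of Week 36, Week 48, and Week 52". SAP 9 and 9.4 tabulate endpoints at each scheduled visit, and 9.4 makes NRI the primary method for proportions. Continuous endpoints are not imputed (SAP 5.5.4).

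**The concern.** The general rule and its mechanics can give different answers for the same patient at the same visit. The by-visit rates serve the Extension objective in protocol 6.1.4, which asks how well clinical improvement is kept up. In a single-arm trial, a response that follows rescue and is counted as a success is credited to the study drug. At visits other than Weeks 12 and 52, the literal landmark reading can leave a rate unchanged or raise it, but cannot lower it. Two programmers who each follow a different sentence of 5.5.4 could report different NRI rates from the same data.

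**Working it through.** **Inputs.** Ideal analysis days from SAP Table 4; about 60 patients (SAP 4.1 and 5.1); one ITT population for both periods (SAP 5.4); illustrative rates of 15% and 30% (SAP 5.1).

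**The plan's own figures.** SAP 5.1 gives 95% CI half-widths at n = 60. With 1.96 × √(p(1 − p)/n):
- p = 0.15: 1.96 × √(0.15 × 0.85/60) = 9.0 points
- p = 0.30: 1.96 × √(0.30 × 0.70/60) = 11.6 points

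Both reproduce. They are used below only for scale.

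**The two rules, for a first failure on day d.**
- Rule A (opening sentence): non-response at every visit after d.
- Rule B (mechanics): non-response from Week 12 if d is no later than Day 85, and from Week 52 if d is no later than Day 365. Using the ideal day as the cut-off is an assumption, because the SAP does not define it.

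| Failure day | Non-response under A but not under B |
|---|---|
| 10 | Weeks 4, 8 |
| 40 | Week 8 |
| 70 | none |
| 120 | Weeks 24, 36, 48 |
| 200 | Weeks 36, 48 |
| 260 | Week 48 |
| 340 | none |
| 400 | all nine visits, Weeks 64 to 160 |
| 600 | Weeks 88 to 160 (seven visits) |

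For example, a patient who starts antibiotics for a flare on Day 120 and responds at Week 24 is a non-responder under A. Under B the patient is not a Week 12 failure and the Week 52 imputation has not begun, so the response stands.

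**How many visits.** Table 4 has 16 post-baseline treatment visits. The rules can differ at 2 (Weeks 4, 8) + 3 (Weeks 24, 36, 48) + 9 (Weeks 64 to 160) = 14. This is a ceiling for diary and CDAI endpoints. Protocol Tables 2 and 3 schedule post-baseline colonoscopy and biopsy only at Weeks 12 and 52 or early termination.

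**Weeks 12 and 52.** The rules agree when failure precedes the visit. They need not agree for a rescue on or just after the visit day. If such a patient is classed as a Week 12 failure, B makes Week 12 itself a non-response, while A keeps a response that came before the rescue. The SAP does not say whether the cut-off is the visit date, Day 85, or the end of the window (Day 98 for Week 12).

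**Size per patient.** 1/60 = 1.7 points, 2/60 = 3.3, 3/60 = 5.0. As an illustration with assumed counts, 18/60 = 30.0% becomes 15/60 = 25.0% if three responders had been rescued. Matching the half-widths would take 9.0/1.67 = 5.4 and 11.6/1.67 = 6.96, so 6 to 7 such patients at one visit. The number on corticosteroids at baseline is not given; if it is 15 to 30 (assumption), one patient moves that rate by 1/15 = 6.7 to 1/30 = 3.3 points.

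**The case against.** The best defence is that 5.5.4 states a general rule and then defines it: failure status is fixed at Week 12 and Week 52 and carried forward, and the opening sentence uses the term in that sense. The word *only* is in neither landmark sentence; that they limit the rule is an inference. On this view the SAP is under-specified between landmarks and after Week 52, not in conflict. The inference is still the more natural one. If the landmark sentences merely illustrated the opening rule they would be nearly redundant, and 9.1 provides no failure status for any other visit. If they define the rule, rescued patients count as responders in the by-visit tables.

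A second defence is the remark in SAP 9.4 restricting something to Weeks 12 and 52. It follows the confidence-interval sentence and most plainly limits the intervals, although a wider reading is possible. The same section tabulates proportions at every scheduled visit, and carrying imputation beyond Week 52 would serve no purpose without later NRI results. However, the NRI graphs in 4.2.3 are at Weeks 12 and 52 only, so the affected outputs are tables, without planned intervals on the plain reading.

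Third, the reach is limited. Patients who leave for alternative therapy are already non-responders through missing data. Observed-case analyses and a listing of failures are planned, and no hypothesis is tested. All of this stands. It does not settle failure timing: the observed-case analysis addresses missing data, and the treatment-failure sensitivity analysis in SAP 12 covers endoscopic endpoints.

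Finally, the body of SAP Table 6 and Section 9.5 could not be read in the text available, and 4.2.3 names no method for corticosteroid-free remission. A timing rule in either place could narrow the point.

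**Conclusion.** The point holds as a minor one. The opening sentence of SAP 5.5.4 and its landmark mechanics, taken literally, classify some rescued patients differently at visits other than Weeks 12 and 52. It concerns mainly CDAI, PRO2 and SF&AP response and remission. Corticosteroid-free remission at Weeks 36 and 48 may also be affected, where the rescue was not a steroid (antibiotics or dilation, for example) and if the general NRI rule applies to it. Weeks 4 and 8 matter least, because the protocol's induction proportions are at Week 12.

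The effect is 1.7 points per patient and visit at n = 60. The total is unknown: the documents give neither a rescue rate nor the number of failures who stay on study.

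Three stronger readings are not supported. A reader might infer that the main results are compromised; but the Week 12 and Week 52 proportions agree under both rules when failure precedes the visit, and the continuous primary endpoint is not imputed. A reader might infer that all endpoints are exposed at 14 of 16 visits; endoscopy and histology are not scheduled at those visits, apart from early termination. And a reader might infer that failures are dropped from the analysis; the SAP counts them as non-responders and keeps them in the denominator.

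**What to change.** Keep the Week 12 and Week 52 sentences and add to SAP 5.5.4 and 9.1: *The clinical review also records the date of first treatment failure through Week 160; in all NRI analyses the patient is a non-responder at every other scheduled visit assessed after that date.* State as well whether failure at Week 12 or Week 52 means failure by the visit date or by the end of the analysis window.

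Keeping the landmark sentences matters. Replacing them with a rule based only on visits after the failure date could turn a patient rescued on the visit day into a Week 12 or Week 52 responder.

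The cost is SAP wording, a modest extension of the internal clinical review, and slightly lower by-visit rates where rescued responders exist.

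Alternative: limit the treatment-failure clause of the opening sentence to Weeks 12 and 52 onwards, keep NRI for missing data at all visits, and footnote the other by-visit tables as including responses after treatment failure. This costs wording and a footnote, but leaves those responses counted as successes.
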